7.3.5. Tests/clinical laboratory tests

Enter whether or not tests are implemented and test results for the clinical course from before administration of this drug to the last day of the observation period. Before administration of this drug, enter the latest test results for tests implemented during the period from three months before the start of administration to immediately before the start of administration (including the start date of administration) (For cardiac function tests: from six months before the start of administration). At the end of the observation period, enter the test results within one month after the last day of the observation period. If there are no test results for appropriate dates, enter the test results for the day of tests closest to the last day of the observation period. For any test results, enter the implementation date and test results. Regarding clinically-problematic abnormal changes in test values compared to the values before the start of administration, enter the details in the section of adverse events as well.

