7.2.6. Observation period

7.2.6.1. Observation period

One year (52 weeks) from the start date of administration.

However, in patients who discontinue treatment with this drug, the period will be from the start date of administration to the first consultation day after the discontinuation day of treatment with this drug.

[figure not shown]

Figure 1. Observation Period for Each Booklet

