8. STATISTICAL METHODS AND ANALYSES

Unless otherwise stated, for patients who completed treatment, data within the first 52 weeks (364 days) + 30 days (= 394 days) will be included in each statistical analysis. For patients who discontinued treatment, data until the first visit after discontinuation of treatment with Selara tablets, or the date 30 days after the last treatment, whichever comes first, will be included. For patients who died, all data will be included.

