8.2.3.3. Other Endpoints

Observed values and changes from baseline at each Visit specified in Appendix A1.1 will be analyzed according to "8.1.1 Continuous Variables" for the following variables:

• Blood pressure (systolic, diastolic).

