11. APPENDICES

11.1. Appendix 1: Details of Data Extraction

A1.1 Definition of Visits for the Assessment of Dosing Status and Safety Endpoints

Visit	Endpoints	Representative date	Definition (time window)	
Baseline	Dosing status, safety endpoints	Day 1	From 30 days before the date of the first dose in this study (the date of the start of	
	outry trapellie		treatment) to the date of treatment start (before dosing)	
Week 1	Dosing status,	Day 7	From the date of treatment start (after	
	safety endpoints		dosing) to 17 days after treatment start	
Week 4	Dosing status, safety endpoints	Day 28	18-42 days after treatment start	
Week 8	Dosing status, safety endpoints	Day 56	43-70 days after treatment start	
Week 12	Dosing status, safety endpoints	Day 84	71-98 days after treatment start	
Week 16	Dosing status, safety endpoints	Day 112	99-126 days after treatment start	
Week 20	Dosing status, safety endpoints	Day 140	127-154 days after treatment start	
Week 36	Dosing status, safety endpoints	Day 252	155-266 days after treatment start	
Week 52	Dosing status, safety endpoints	Day 364	267-394 days after treatment start	
Final	Dosing status,		The time when the final visit for this study	
Visit	safety endpoints		is made	

If multiple sets of observation data are reported on different dates within a time window, data on the date closest to the representative one will be used for summarization/analysis. If two sets of data are reported on two dates equally close to the representative one, the data on the later date will be adopted. If there are multiple values observed on the same day, the mean value of them will be used.

A1.2 Definition of Visits for Cardiac Function Classification

Visit	Endpoints	Representative Date	Definition (time window)
Baseline	Left ventricular ejection fraction (LVEF), left ventricle internal dimensions in diastole (LVDd), left atrial dimension (LAD)	Day 1	From 180 days before the date of the first dose in this study (the date of the start of treatment) to the date of treatment start (before dosing)
Week 26	LVEF, LVDd, LAD	Day 182	From the date of the start of treatment (after dosing) to 182 days after treatment start
Week 52	LVEF, LVDd, LAD	Day 364	183-394 days after treatment start

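### Blood pressure at Final Visit pools readings taken after stopping the drug with readings taken on it, and the SAP does not separate them

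*Protocol*

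**What the plan says.** **Collection.** For a patient who discontinues, Protocol 7.2.6.1 says "the period will be from the start date of administration to the first consultation day after the discontinuation day of treatment with this drug". Protocol 7.3.5 has sites enter "test results for the clinical course from before administration of this drug to the last day of the observation period", so readings during treatment are recorded too. For the closing test the rule is "At the end of the observation period, enter the test results within one month after the last day of the observation period". If no such test exists, sites are to "enter the test results for the day of tests closest to the last day of the observation period".

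**Data cut.** For completers, SAP 8 says "data within the first 52 weeks (364 days) + 30 days (= 394 days) will be included in each statistical analysis". For patients who discontinue, it includes "data until the first visit after discontinuation of treatment with Selara tablets, or the date 30 days after the last treatment, whichever comes first". For patients who die, all data are included.

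**Analysis.** SAP 8.2.3.3 plans "Observed values and changes from baseline at each Visit specified in Appendix A1.1" for systolic and diastolic pressure. Appendix A1.1 defines eight post-baseline windows plus Final Visit, whose definition begins "The time when the final visit for this study". That definition refers neither to dosing nor to the data cut. Within a window, the reading nearest the representative date is used, and the later one on a tie.

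**Treatment status.** SAP 5.4 lists completed versus discontinued as a subgroup for effectiveness but not for safety. SAP 8.2.2 leaves Final Visit out of the dosing summaries by period. SAP 8.2.3.3 does not leave it out for blood pressure.

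**The concern.** Read together, these rules put two kinds of reading in one row. A completer's Final Visit reading is taken on the drug. A stopper's reading may have been taken up to 30 days after the last treatment. Nothing in the blood pressure summary tells the reader which is which.

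Protocol 6.1 names events related to hypotension as an important identified risk. Of the safety measurements in SAP 6.1 (blood pressure, body weight, creatinine, potassium, BUN), only blood pressure has a planned summary by visit; the others are only listed (SAP 9). Patients who stop leave the later windows, so Final Visit is the row a reader would turn to for the end-of-treatment change in everyone. If stoppers' pressure has moved back towards baseline by then, the row shows a smaller fall than these patients had on the drug.

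**Working it through.** The plan states no figure for this point, so there is none to reproduce. Its one piece of arithmetic, 364 + 30 = 394 days, is correct.

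**Step 1: follow one stopper through the rules.** Let the last treatment be on day s and the first consultation after it on day V.
- Observation ends on day V (Protocol 7.2.6.1).
- If V ≤ s + 30, SAP 8 keeps the reading at V and nothing later. That reading is off drug and is the patient's last analysable one, so it becomes Final Visit.
- If V > s + 30, SAP 8 drops the reading at V. Appendix A1.1 does not say whether Final Visit then falls back to an earlier reading.

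**Step 2: how often V lies inside the cut.** The documents fix no visit interval. Assume visits every k days, a reading at each, and a last dose on any of days 1–335 irrespective of the visit dates. The share inside the cut is min(1, 30/k). Enumerating all offsets also gave the share of those readings that become the value for their scheduled window under the nearest-date rule.

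| Visit interval k | V inside the 30-day cut | Of those, used in its window |
|---|---|---|
| 14 days | 100% | 87% (Weeks 1–20: 74%; Weeks 36 and 52: 96%) |
| 28 days | 100% | 100% |
| 42 days | 30/42 = 71% | 100% |
| 56 days | 30/56 = 54% | 100% |
| 84 days | 30/84 = 36% | 100% |

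If the drug is instead stopped at a visit, the next consultation is a full interval later. It is then inside the cut at 14 or 28 days and outside it at 42 days or more, unless an extra visit occurs.

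**Step 3: size, under stated assumptions.** Let p be the share who stop, c the share of stoppers whose off-drug reading is used, and g their mean recovery after stopping. If the remaining stoppers contribute an on-drug reading, then

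understatement at Final Visit = p × c × g.

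The documents give none of the three. Taking p = 0.15–0.40 and g = 4–8 mmHg:
- c = 1: from 0.15 × 1 × 4 = 0.6 to 0.40 × 1 × 8 = 3.2 mmHg.
- c = 0.36: from 0.15 × 0.36 × 4 ≈ 0.2 to 0.40 × 0.36 × 8 ≈ 1.2 mmHg.

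**Step 4: direction.** Let d be the share of the row that is off drug, and r those patients' change divided by the change in patients still on drug. The pooled change, as a multiple of the latter, is (1 − d) + d × r.

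| r | d = 0.10 | d = 0.40 |
|---|---|---|
| 0 (back at baseline) | 0.90 | 0.60 |
| 0.5 | 0.95 | 0.80 |
| 1 | 1.00 | 1.00 |
| 1.5 | 1.05 | 1.20 |

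So the row need not look smaller than the completers' change. A multiple above 1 does not by itself rule out understatement, though. A stopper who fell further than others on the drug and then partly recovered can have r above 1, while the row still understates that patient's own on-drug fall. What matters is whether pressure recovers within the patient after stopping.

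**The case against.** The strongest case on the other side is that little depends on this table. Hypotension is assessed mainly through hypotension-related events, with action taken, outcome and onset time (SAP 8.2.3.1). Clinically problematic test changes must also be entered as adverse events (Protocol 7.3.5). The blood pressure summary is descriptive, SAP 4.2 has no decision rule, and individual readings are listed (SAP 9). Stoppers' earlier on-drug readings also stay in the windows before they stop. All of this stands. It limits the consequence but does not make the mixed row readable.

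A reader might also infer more than the documents support:
- **That every stopper contributes an off-drug reading.** The nearest-test fallback can supply an earlier on-drug reading. Protocol 7.3.3 lists failure to return as a reason for stopping. SAP 8 removes a first visit more than 30 days after the last treatment. A patient who dies on the drug has no visit after stopping.
- **That readings up to a month after that visit are analysed.** The one-month allowance in 7.3.5 governs data entry. By default, SAP 8 cuts a stopper's data at the first visit after stopping.
- **That the reading always enters its scheduled window.** It does so only when it is nearest the representative date.
- **That understatement is certain.** The protocol refers to an antihypertensive action and links hypotension to the drug's mechanism, so some recovery is the natural expectation. No passage reports pressure after stopping. Worsening heart failure or added therapy could keep it low.
- **That moderate renal impairment is hit hardest.** No stopping rate by renal function is given. SAP 8.2.3.3 plans no blood pressure table by subgroup, and SAP 8.2.3.4 covers only adverse reactions, serious adverse reactions and SAEs.

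**Conclusion.** The point holds in a limited form. Followed as written, the plan lets off-drug readings up to 30 days after the last treatment into the Final Visit blood pressure row and, conditionally, into scheduled windows, with nothing to separate them from on-drug readings. With visits every 14 or 28 days this would be routine among stoppers who return; with longer intervals it would affect only some of them.

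The size is unknown. The 0.6–3.2 mmHg range, or about 0.2–1.2 mmHg when only 36% of stoppers contribute, is arithmetic on assumed stopping rates and recoveries, not an estimate. Understatement of the fall on treatment is the likely direction but is not established. The case for change is that a safety table for an important identified risk cannot be interpreted as planned, and that separating the readings is cheap. The adverse-reaction analyses are unaffected.

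**What to change.** Amend SAP Appendix A1.1 and 8.2.3.3 as follows:
- Add a row for the last on-treatment value, with change from baseline: the last reading dated from after the first dose to the date of last dose.
- Keep Final Visit, but present it split into completed and discontinued.
- State that Final Visit follows the SAP 8 data cut.
- Where SAP 8.2.2 has imputed an unknown last-dose date as the first visit after stopping, do not count that visit's reading as on treatment. Otherwise the imputation would relabel an off-drug reading.
- Optionally, give the scheduled windows restricted to on-treatment readings as a supplementary summary.

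The cost is SAP wording, one extra row and one split. Treatment periods (Protocol 7.3.2) and test dates (7.3.5) are already collected, and nothing is removed from the plan. Two limits remain. A few early stoppers will have no on-treatment reading. Temporary interruptions will still count as on treatment, as they already do in the SAP 8.2.2 definition of treatment duration.

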7.2.1. Inclusion criteria

Patients in whom treatment with this drug is for CHF

The Indication, and Dosage and Administration at approval for this drug are as follows. When using this drug, refer to the latest package insert of this drug.

[Indication]

Patients currently receiving angiotensin-converting enzyme inhibitor or angiotensin II receptor antagonist, β blocker, diuretic, or other products as a standard treatment of:

Chronic Heart Failure

[Dosage and Administration]

In adults, usually, administer the initial dose of 25 mg once daily, and according to the patient's conditions and serum potassium level, increase dosage up to 50 mg once daily after 4 weeks; patients with moderate renal impairment should start with 25 mg once every other day and the maximum dosage should be 25 mg once daily.

Also, dose should be reduced or interrupted according to serum potassium level and patient's conditions.

[Precautions for Dosage and Administration]

- (1) Patients with moderate renal impairment (a creatinine clearance more than 30- less than 50 mL/min) should commence on 25 mg of this drug once every other day and dosage can be increased up to 25 mg once daily after 4 weeks depending on the serum potassium level and patient's condition. The maximum dosage should be 25 mg once daily. [Regarding to the adjustment based on eGFR used in clinical studies, see "Clinical studies"]
- (2) Serum potassium should be monitored periodically. Adjust the dosage in accordance with Table 1. [See "Important Precautions"]

Table 1. Adjustment of Dosage and Administration according to Serum Potassium Level

Serum Potassium Level (K+) mEq/L	Adjustment of Dosage and Administration
less than 5.0	In the case of 50 mg once daily: Maintain In the case of 25 mg once daily: Increase to 50 mg once daily In the case of 25 mg every other day: Increase to 25 mg once daily
5.0-5.4	Maintain
5.5-5.9	In the case of 50 mg once daily: Decrease to 25 mg once daily In the case of 25 mg once daily: Decrease to 25 mg every other day In the case of 25 mg every other day: Withhold
not less than 6.0	Withhold

It can be restarted at a dose of 25 mg every other day when K+ has fallen below 5.0 mEq/L.

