Note: Adverse events are any and all unfavorable events (including clinically significant abnormal changes in laboratory tests) occurring in patients after starting treatment with this drug regardless of their causal relationship. Serious adverse events are any unfavorable medical occurrences that result in death, are life-threatening, require (or prolong) hospitalization, cause persistent or significant disability/incapacity, result in congenital anomalies or birth defects, or are other conditions which represent significant health hazards.

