9.1. Requirements

The table below summarizes the requirements for recording safety events in the CRF and for reporting safety events by the NIS AE Report Form to Pfizer Safety. These requirements are delineated for three types of events: (1) serious adverse events (SAEs); (2) non-serious AEs (as applicable); and (3) scenarios involving drug exposure, including exposure during pregnancy, exposure during breastfeeding, medication error, overdose, misuse, extravasation, and occupational exposure. These events are defined in the section "Definitions of safety events."

Safety event	Recorded on the data collection tool (e.g. CRF)	Reported on the NIS AE Report Form to Pfizer Safety within 24 hours of awareness
SAE	All	All
Non-serious AE	All	None
Scenarios involving exposure to a drug under study, including exposure during pregnancy, exposure during breastfeeding, medication error, overdose, misuse, extravasation, lack of efficacy, and occupational exposure	All (regardless of whether associated with an AE), except occupational exposure	All (regardless of whether associated with an AE)

For each AE, the investigator must pursue and obtain information adequate both to determine the outcome of the AE and to assess whether it meets the criteria for classification as a SAE (refer to section "Serious Adverse Events" below).

Safety events listed in the table above must be reported to Pfizer within 24 hours of awareness of the event by the investigator regardless of whether the event is determined by the investigator to be related to a drug under study. In particular, if the SAE is fatal or life-threatening, notification to Pfizer must be made immediately, irrespective of the extent of available event information. This timeframe also applies to additional new (follow-up) information on previously forwarded safety event reports. In the rare situation that the investigator does not become immediately aware of the occurrence of a safety event, the investigator must report the event within 24 hours after learning of it and document the time of his/her first awareness of the events.

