9.4. Definitions of safety events

9.4.1. Adverse events

An AE is any untoward medical occurrence in a patient administered a medicinal product. The event need not necessarily have a causal relationship with the product treatment or usage.

- Abnormal test findings (see below for circumstances in which an abnormal test finding constitutes an adverse event);
- Clinically significant symptoms and signs;
- Changes in physical examination findings;
- Hypersensitivity;
- Progression/aggravation of underlying disease;
- Lack of efficacy;
- Drug abuse;
- Drug dependency.

Additionally, for medicinal products, they may include the signs or symptoms resulting from:

- Drug overdose;
- Drug withdrawal;
- Drug misuse;
- Off-label use;
- Drug interactions;
- Extravasation;
- Exposure during pregnancy;
- Exposure during breastfeeding;
- Medication error;
- Occupational exposure.

Abnormal test findings

The criteria for determining whether an abnormal objective test finding should be reported as an AE are as follows:

- Test result is associated with accompanying symptoms, and/or
- Test result requires additional diagnostic testing or medical/surgical intervention, and/or
- Test result leads to a change in study dosing or discontinuation from the study, significant additional concomitant drug treatment, or other therapy, and/or
- Test result is considered to be an AE by the investigator or sponsor.

Merely repeating an abnormal test result, in the absence of any of the above conditions, does not constitute an AE. Any abnormal test result that is determined to be an error does not require reporting as an AE.

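### Two unreconciled rules decide when a laboratory value is an adverse event, and no planned summary would show potassium-driven dose reductions or interruptions left off the AE page

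*Protocol*

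**What the plan says.** **Section 7 of the protocol.** Section 7.3.5 asks sites to enter test results and, introduced by "Regarding clinically-problematic abnormal changes in test values compared to the values before the start of administration", to give the details on the AE page too. The note to 7.3.8 describes AEs as "including clinically significant abnormal changes in laboratory tests". Neither section defines its adjective by a value or an action.

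**Section 9 of the protocol.** Section 9.4.1 lists alternative criteria, any one of which is enough. One is "Test result leads to a change in study dosing or discontinuation from the study". Another is "Test result is considered to be an AE by the investigator or sponsor". Section 9.1 says that its table "summarizes the requirements for recording safety events in the CRF and for reporting safety events by the NIS AE Report Form to Pfizer Safety", and that table requires every non-serious AE to be recorded in the CRF.

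**The quoted label.** Table 1 in 7.2.1 ties potassium of 5.5 to 5.9 mEq/L to a step down or, at the lowest step, withholding (for example "In the case of 50 mg once daily: Decrease to 25 mg once daily"), and 6.0 or more to withholding.

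**SAP.** Section 6.1 builds the hyperkalaemia item from AEs that the physician has marked as hyperkalaemia-related in the CRF, with no potassium threshold. It also names serum potassium as a safety endpoint. Section 8.2.3.3, which covers the other safety endpoints by visit, names only blood pressure.

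**The concern.** Hyperkalaemia is an important identified risk and a major investigation item. Its assumed rate in moderate renal impairment is one of the two used to justify the sample size, and comparing the safety profile with the clinical studies is a stated aim of that sample size (Protocol 7.5.2).

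The numerator depends wholly on what 150 planned sites put on the AE page. If one section leaves an acted-upon potassium value to judgement and another makes it an AE outright, two sites can read the protocol in good faith and record the same patient differently. A low hyperkalaemia figure could then partly reflect recording practice, and nothing in the planned tables would let the reader tell.

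**Working it through.** **1. The plan's own figure.** Table 5 gives hyperkalaemia in moderate renal impairment as 2 of 37 and 20 of 224 patients, so (2 + 20)/(37 + 224) = 22/261 = 8.4%.
- Expected events: 300 × 0.084 = 25.2 and 350 × 0.084 = 29.4, as stated in 7.5.2.
- Standard error at 300 patients: √(0.084 × 0.916/300) = 1.60 percentage points.
- Range: 8.4 ± 1.96 × 1.60 = 5.3% to 11.5%, as stated.

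The figures reproduce. They describe sampling error and say nothing about incomplete recording.

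**2. The two rules side by side.**
- *Trigger:* 7.3.5 and the 7.3.8 note use a clinical judgement. In 9.4.1 a dosing change is enough by itself.
- *Reference point:* 7.3.5 compares with the value before treatment. 9.4.1 has no baseline reference.
- *Scope:* both reach the CRF, the Section 7 wording directly and 9.4.1 through 9.1.
- *Precedence:* none is stated, and 7.3.5 and 7.3.8 do not refer to 9.4.1.

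**3. One case traced through.** Take a patient without symptoms, with potassium between 5.5 and 5.9 mEq/L, whose dose is changed in line with the quoted Table 1 ("In the case of 25 mg once daily: Decrease to 25 mg every other day"). Under 9.4.1 this is an AE because the dose changed. Under the Section 7 wording taken alone, it depends on whether the physician thinks the change from baseline is a problem. Suppose it is not entered as an AE. Then:
- SAP 6.1 and the major-item table in 8.2.3.1 do not count it, since there is no AE to flag.
- The action-taken tables in 8.2.3.1 run over recorded events, so it is absent there too.
- The dosing tables in 8.2.2 give mean daily dose by eCLCr group, but give reasons only for discontinuation, not for reductions or interruptions.
- SAP 8.2.3.3 does not summarise potassium.
- The listings in SAP Section 9 show the potassium value line by line. The dosage listing covers only patients who already have a recorded hyperkalaemia reaction.

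**4. Where the gap lies.** Protocol 7.3.3 tells sites to give AE details when an AE is the reason for discontinuation. Protocol 7.3.2 asks for the reason for a dose change but carries no such instruction. The exposure is therefore mainly in reductions and interruptions.

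**5. Size.** It would require the share of hyperkalaemia cases known only from a potassium value and a dose change, and the share of those left off the AE page. The documents give neither, so no estimate is offered.

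**The case against.** The strongest reply is that the sections are compatible: Section 7 is general wording and 9.4.1 supplies the operational definition. Much of this stands. The 7.3.8 note is inclusive, 7.3.5 asks for AE entry in addition to the test entry, and neither says that other laboratory changes are not AEs. A site applying all of Section 9 would record every potassium value that led to a dose change. Sponsor queries (7.6.3.2) and the sponsor's power under 9.4.1 to deem a result an AE are further safeguards. Section 7.9 also discloses that data may be missing.

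Four stronger readings are tempting, and the documents do not support them:
- *That Section 7 excludes such events.* It contains no such restriction.
- *That hyperkalaemia is in fact counted at some sites and not at others.* This is possible but nowhere shown. A recorded AE must also be marked as hyperkalaemia-related, which is a separate judgement.
- *That nothing links a dose change to an AE.* Section 9.4.1 does, and 7.3.3 does so for discontinuation.
- *That the comparison with 8.4% is biased by a known amount.* The documents do not say how the two trials classed laboratory findings, so even the direction is uncertain. The 8.4% also counts only events judged possibly drug-related.

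What the reply leaves untouched is that no sentence states the compatible reading, and that no planned summary would show whether sites followed it.

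**Conclusion.** The point holds as a gap in ascertainment and in its visibility, not as a demonstrated bias. Two criteria for a laboratory AE apply to one CRF without express reconciliation, so asymptomatic potassium-driven reductions or interruptions could go unrecorded at sites that rely on Section 7. The hyperkalaemia count would inherit any such omission, and the planned summaries would not expose it.

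The size is unknown and cannot be derived from the documents. The sample-size figures are unaffected. The conclusion assumes only that some sites may read 7.3.5 and 7.3.8 without 9.4.1. This is a cheap improvement rather than a flaw that undermines the study.

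**What to change.** 1. **Protocol wording.** Reconcile the passages by having 7.3.5 and the 7.3.8 note refer to the 9.4.1 criteria. SAP version 7.0 marks observation as completed, so this cannot change how sites first entered data, but it settles which rule the report should cite.
2. **SAP 8.2.3.1.** Keep the current hyperkalaemia count. Beneath it, by eCLCr group, add a supplementary row for patients with a hyperkalaemia-related AE, or a dose reduction or interruption with potassium as the recorded reason. Show how many of those dose changes have no recorded AE.
3. **SAP 8.2.3.3.** Beside it, summarise on-treatment serum potassium in fixed categories by eCLCr group, for instance the bands already used in Table 1. Use each patient's highest value, because the visit windows in Appendix A1.1 keep only the reading nearest the representative date, and give the number of patients with any on-treatment value.
4. **Optional.** A data check for potassium-related dose changes without a matching AE. It is of limited use now that observation is complete.

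The SAP items use data that Protocol 7.3.2 and 7.3.5 already collect. The cost is a little programming, some coding if reasons were entered as free text, and possibly a slightly higher supplementary figure. That row has no counterpart in Table 5, so it is a sensitivity check and does not replace the comparison with 8.4%.
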